8.3. Subject Exclusion Criteria

1. Any history or presence in the last 30 days, before rolling over to this study, of other concomitant liver diseases, including any of the following:
 - Hepatitis C virus (HCV) infection with positive RNA
 - Active hepatitis B virus (HBV) infection; however, subjects who have seroconverted (hepatitis B surface antigen negative [sAg-], hepatitis B surface antibody positive [sAB+]; hepatitis B e-antigen negative [eAg-], hepatitis B e-antibody positive [eAb+]; HBV DNA negative) may be included in this study after consultation with the Medical Monitor and Sponsor Medical Monitor
 - Subjects should be excluded if positive HBV DNA or HCV RNA
 - PSC
 - Alcoholic liver disease
 - Definite autoimmune liver disease or PBC-AIH overlap
 - MASH
 - Gilbert's Syndrome (due to interpretability of bilirubin levels)
 - Rare liver conditions such as Wilson's disease, hemochromatosis, alpha-one anti-trypsin deficiency, or other conditions identified by the Principal Investigator
2. Clinical complications of PBC including:
 - Prior liver transplantation
3. Any history or presence in the last 30 days, before rolling over to this study, of any one of the following decompensating events:
 - CP Score ≥ 7
 - Clinical evidence of decompensated liver disease or evidence of portal hypertension, including but not limited to:
 - Varices (including a history of esophageal varix ligation or asymptomatic esophageal varices by endoscopy)
 - Ascites/hepatic hydrothorax
 - Spontaneous bacterial peritonitis
 - Hepatic encephalopathy
 - Jaundice (with total bilirubin >3 mg/dL [>51.3 $\mu\text{mol/L}$])
 - Biochemical evidence of hepatic impairment, decompensation, or injury including at least one of the following:
 - Total bilirubin $>\text{ULN}$

- INR >1.7
 - Albumin <3.5 g/dL
 - MELD >12
 - ALT >5x ULN
 - Known or suspected HCC
 - Prior trans-jugular intrahepatic portosystemic or peritoneovenous shunt procedure
 - Hepatorenal syndrome (type I or II) or serum creatinine >1.5 mg/dL (135 µmol/L) or estimated glomerular filtration rate (eGFR) <60 mL/min from the last lab assessment/visit in parent study, before transitioning to Study 977-311
 - Portopulmonary hypertension
 - Hepatopulmonary syndrome
4. Medical conditions that may cause non-hepatic increases in ALP (e.g., Paget's disease) or that may diminish life expectancy to <2 years, including known cancers (except carcinomas in situ or other stable, relatively benign conditions)

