 5. Presence of any other disease or condition that interferes with the absorption, distribution, metabolism, or excretion of drugs including bile salt metabolism in the intestine (e.g., inflammatory bowel disease or gastric bypass procedure [gastric lap band is acceptable])
 6. Evidence or history of cholelithiasis or choledocholithiasis unless documented cholecystectomy. Gallbladder polyps if >5 mm in diameter
 7. History of chronic pancreatitis or recurrent acute pancreatitis – defined as at least 2 episodes of acute pancreatitis, with symptoms resolving between each episode
 8. History of drug-induced myopathy
 9. Chronic kidney disease (serum creatinine >1.5 mg/dL [>135 µmol/L]; CrCl <60 mL/min) or undergoing dialysis
 10. Platelet count <150,000/µL at the last visit in parent study, before transitioning to Study 977-311
 11. Known history of human immunodeficiency virus (HIV) infection
 12. History or presence of clinically concerning cardiac arrhythmias likely to affect survival during the study, QT interval of the electrocardiogram (QT) or QT interval of the electrocardiogram corrected (QTc) interval of >450 milliseconds for males and >470 milliseconds for females
 13. Severe pruritus, or required systemic treatment for pruritus (e.g., with bile acid sequestrants [BAS] or rifampicin) within 2 months of Day 1 of Study 977-311. Subjects who plan to use or will use BAS during the study will not be eligible.
 14. History of known or suspected clinically significant (CS) hypersensitivity to OCA, BZF, or other fibrates or any of their components

15. Known photoallergic or phototoxic reactions to fibrates
16. If female, known pregnancy, a positive urine pregnancy test (confirmed by a positive quantitative serum pregnancy test), or current lactation at the last visit in parent study, before transitioning to Study 977-311
17. Other CS medical conditions that are not well controlled or for which medication needs are anticipated to change during the study (e.g., Type 2 diabetes mellitus, hypothyroidism, nephritic or nephrotic syndrome, dysproteinemia, obstructive biliary disease, dyslipidemia), and/or up to the discretion of the Principal Investigator

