Blood samples for determining the plasma concentrations of OCA and BZF and their metabolites will be collected in this study.

Laboratory analyte results may be used to calculate various cardiovascular risk and fibrosis measurement scores.

The list of laboratory analytes to be tested is shown in Table 11.

Table 11: List of Laboratory Scores and Analytes

Laboratory Assessment	Scores and Analytes ^a
Serum chemistry	Albumin, ALP, BUN, creatinine, conjugated (direct) bilirubin, total bilirubin, AST (SGOT), ALT (SGPT), GGT, electrolytes [calcium, chloride, potassium, sodium], glucose, total protein, and blood lipids (total cholesterol, LDL, HDL and VLDL fractions and TG, magnesium, phosphorus, bicarbonate, unconjugated (indirect) bilirubin, free fatty acids, eGFR, CK, and CrCL
Hematology	Hemoglobin, hematocrit, white blood count with differential (neutrophils, lymphocytes, monocytes, eosinophils, basophils), platelets, and red blood cell count (including MCV, MCH, MCHC)
Urinalysis	pH, specific gravity, protein, glucose, ketones, bilirubin, blood, microscopic exam, creatinine, albumin, leukocytes, nitrates, and albumin/creatinine ratio (if positive)
Coagulation	PT, aPTT, INR
Noninvasive measurement of liver stiffness	ELF, and markers of [REDACTED] TE
Virology	HCV, HBsAg
Pregnancy test (female subjects of childbearing potential) ^b	β -hCG
Disease Severity Scores	MELD, CP, GLOBE and UK-PBC scores
PD assessment	[REDACTED]
PK assessment	BZF, OCA and their metabolites

[REDACTED]; aPTT=partial thromboplastin time; β -hCG=beta-human chorionic gonadotropin; BUN=blood urea nitrogen; BZF=bezafibrate; [REDACTED] CrCL=creatinine clearance; CK=creatinine kinase; CP=Child-Pugh score; eGFR=estimated glomerular filtration rate; ELF=enhanced liver fibrosis; HBsAg=hepatitis B surface antigen; HCV=hepatitis C virus; HDL=high-density lipoprotein; INR=international

normalized ratio; LDL=low-density lipoprotein; MCH=mean corpuscular hemoglobin; MCHC=mean corpuscular hemoglobin concentration; MCV=mean corpuscular volume; MELD=model of end-stage liver disease; OCA=obeticholic acid; PD=pharmacodynamic; PK=pharmacokinetic; [REDACTED] PT=prothrombin time; TE=transient elastography; TG=triglycerides; UK=United Kingdom; VLDL=very-low-density lipoprotein

^a Overlapping analytes will be analyzed only once.

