5.5. Analysis Windows

Analysis windows will not be defined in this study. Only the scheduled visits will be included in the analyses. All visits, including unscheduled visits, will be presented in the listings.

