10.3. Clinical Laboratory Evaluations

Laboratory parameters will be summarized in both conventional and standard international system of units using descriptive statistics at Baseline and at each on-study evaluation. Baseline is defined as the mean of all available evaluations prior to the first administration of investigational product.

The normal ranges of the selected lab parameters are defined below. The abnormal indicators of the selected lab parameters will be derived based on these normal ranges (inclusively):

- ALP 44-122 U/L
- ALT 0-45 U/L
- AST 0-45 IU/L
- GGT 0-65 IU/L (male) 0-60 IU/L (female)
- Total Bilirubin 1.71-12.3 umol/L
- Direct Bilirubin 0-0.4 mg/dL
- Cholesterol 0-169 mg/dL (age ≤19), 0-199 mg/dL (age >19)
- LDL 0-109 mg/dL (age ≤19), 0-99 mg/dL (age >19)
- HDL >39 mg/dL
- Creatinine 0.57-1.27 mg/dL
- Creatine 0.0-0.7 mg/dL (male) 0.1-1.0 mg/dL (female)
- CK 41-439 U/L (male, age 18-50 years old), 41-331 U/L (male, age 51-80 years old),

32-182 (female, age 18-80 years old)

For the other lab parameters, the normal ranges and abnormal indicators are based on the values in the data from the central or local labs.

In addition, shift tables (i.e., low-normal-high at Baseline versus low-normal-high at post-Baseline visit in a 3-by-3 contingency table) from Baseline to worst value, last value, and at each scheduled post Baseline visit will be provided for hematology and serum chemistry to assess changes in laboratory values from Baseline to each on-study evaluation from the central or local labs. The subjects meeting Hy's law criteria (defined as AST or ALT ≥ 3 xULN together with total bilirubin ≥ 2 xULN at any timepoint) will be summarized by visit.

Urine chemistry and urinalysis results will not be summarized but will be provided in a data listing.

All clinical laboratory data (including central and local) will be presented in by-subject data listings.

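### SAP 10.3 flags creatinine on one range for both sexes, so its creatinine flags and shift tables are less sensitive in women, who are most of the expected population

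*SAP*

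**What the plan says.** SAP 10.3 (Clinical Laboratory Evaluations) lists normal ranges for 12 selected analytes and takes the abnormal indicators for those analytes from the listed ranges, endpoints included. The creatinine entry reads "Creatinine 0.57-1.27 mg/dL", with no sex split. Three entries in the same list do differ by sex: creatine, CK, and GGT, which reads "GGT 0-65 IU/L (male) 0-60 IU/L (female".

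For analytes outside the list, "the normal ranges and abnormal indicators are based on the values in the data from the central or local labs". Because creatinine is listed, this fallback does not reach it.

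The low-normal-high shift tables run "from Baseline to worst value, last value, and at each scheduled post Baseline visit will be provided for hematology and serum chemistry". SAP 5.5 adds: "Only the scheduled visits will be included in the analyses". Unscheduled creatinine values are therefore listed but do not enter the tables.

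Protocol 14.2.6, Table 11, also places eGFR and creatinine clearance in serum chemistry ("free fatty acids, eGFR, CK, and CrCL"). Neither is in the SAP's list, so both are flagged on laboratory ranges.

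**The concern.** Creatinine is the only filtration marker in the SAP's list. At the same creatinine, a woman generally has lower filtration than a man, so one upper limit flags men at better function than it flags women. The SAP splits other analytes by sex and gives no reason for leaving this one unsplit.

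Renal function matters for this product. Protocol 5.4.2 says bezafibrate exposure rises markedly when creatinine clearance is under 60 mL/min. Protocol 5.6.2, Table 2, links fibrate myositis and rhabdomyolysis mainly to impaired renal function. Long-term safety is the primary objective, and Protocol 5.1 describes PBC as predominantly a disease of women. What is at stake is whether the planned creatinine flags and shift tables show a decline in women as readily as in men.

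**Working it through.** The plan states the range without deriving it, so there is no figure to reproduce. The check asks what 1.27 mg/dL means in each sex.

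**Inputs from the documents.** Upper limit 1.27 mg/dL, inclusive, both sexes (SAP 10.3). About 133 subjects (Protocol 7.2). PBC patients less than 10% male (Protocol 5.1).

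**Assumptions.** The documents name no eGFR or creatinine clearance equation and give no age, weight or creatinine distribution. I use CKD-EPI 2021 and Cockcroft-Gault, with illustrative ages and weights.

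**Step 1, CKD-EPI 2021** (s = creatinine in mg/dL, above 0.7 in women and 0.9 in men):
- Women: 142 × (s/0.7)^−1.2 × 0.9938^age × 1.012
- Men: 142 × (s/0.9)^−1.2 × 0.9938^age

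| Age | Women, eGFR at 1.27 | Men, eGFR at 1.27 | Women's creatinine at eGFR 60 |
|---|---|---|---|
| 45 | 53.1 | 71.0 | 1.15 |
| 55 | 49.9 | 66.7 | 1.09 |
| 65 | 46.9 | 62.7 | 1.03 |
| 75 | 44.1 | 58.9 | 0.98 |

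**Step 2, Cockcroft-Gault in women at 1.27 mg/dL**, 0.85 × (140 − age) × kg / (72 × 1.27), in mL/min:

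| Age | 50 kg | 70 kg | 90 kg |
|---|---|---|---|
| 45 | 44.2 | 61.8 | 79.5 |
| 55 | 39.5 | 55.3 | 71.1 |
| 65 | 34.9 | 48.8 | 62.7 |
| 75 | 30.2 | 42.3 | 54.4 |

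**Step 3, the woman's creatinine that matches a man's function at 1.27 mg/dL.**
- CKD-EPI: 0.7 × (1.27/0.9) × 1.012^(1/1.2) = 0.998 mg/dL. Age cancels.
- Cockcroft-Gault, equal age and weight: 0.85 × 1.27 = 1.080 mg/dL. It is lower if she is lighter.

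Women's values from about 1.00–1.08 up to 1.27 mg/dL are therefore called normal at a level of function that would be flagged in a man. Equivalently, a woman at 1.27 has the function of a man at 1.27 × 1.27/0.998 = 1.62 mg/dL (CKD-EPI) or 1.27/0.85 = 1.49 mg/dL (Cockcroft-Gault).

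**Step 4, the rise needed to be flagged.** From an assumed baseline of 0.7 mg/dL, a woman must rise by more than 1.27/0.7 − 1 = 81%. At the matched limits the rise would be 0.998/0.7 − 1 = 43% or 1.080/0.7 − 1 = 54%.

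**Step 5, how many subjects the weaker flag covers.** If enrolment mirrors the disease, at least 0.9 × 133 = 119.7, or about 120, are women. This counts subjects to whom the flag applies, not subjects who would be misclassified.

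**The case against.** The strongest objections, and what stands of each:

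- **The range may be the laboratory's own.** The SAP does not say where it comes from. If the laboratory reports 0.57–1.27 mg/dL for both sexes, moving creatinine to laboratory ranges changes nothing. This stands as a limit on the fix. It does not make the flag equally sensitive in both sexes.
- **A sex-neutral limit is consistent with the protocol.** Exclusions 3 and 9 in Protocol 8.3 use creatinine above 1.5 mg/dL for everyone, and 9 of the 12 analytes in the SAP's list have no sex split. But those exclusions pair creatinine with filtration limits: "estimated glomerular filtration rate (eGFR) <60 mL/min from the last lab assessment/visit in parent study" and "CrCl <60 mL/min) or undergoing dialysis". The creatinine flag has no such partner.
- **The size is external.** This is correct. The window in step 3 is parity with men, not function under 60 mL/min. By CKD-EPI a woman of 45 reaches 60 only at 1.15 mg/dL. By Cockcroft-Gault a 90 kg woman at 1.27 is still above 60 at ages 45, 55 and 65.
- **Renal safety is covered elsewhere.** This is also correct. The renal AESI is defined by MedDRA queries (SAP 10.2.4.3), potential renal injury is adjudicated (Protocol 14.3), new or worsened laboratory abnormalities suggesting organ toxicity are recorded as adverse events (Protocol 14.2.6), and the DMC reviews laboratory results (Protocol 15.9). None of these is tied to 1.27 mg/dL.

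A reader might infer more: that the plan will miss falls below 60 mL/min. The documents do not support that. eGFR and creatinine clearance are serum chemistry analytes, so they already get descriptive summaries, shift tables to worst value, and listings. If the laboratory's lower limit is 60, the eGFR shift table gives the count directly. If it is 90, a fall from 85 to 55 stays low-to-low. The documents do not state the limit. The protocol uses 60 mL/min at entry and promises no on-study count below it.

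**Conclusion.** The point holds and is minor. Followed as written, SAP 10.3 makes the creatinine flag and shift categories less sensitive in women than in men. Both assumed equations agree on the direction. The gap runs from about 1.00 (CKD-EPI 2021) or 1.08 (Cockcroft-Gault, equal age and weight) up to 1.27 mg/dL. Its size rests on those equations, and its reach on enrolment resembling the disease's sex mix.

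The number of women whose values will fall in the gap cannot be stated from the documents and may be zero. The effect stops at the creatinine flags and shift tables. By-visit creatinine summaries and listings will still show the values themselves, and no hypothesis or sample size is involved. The absence of a stated 60 mL/min table is not part of the error.

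**What to change.** In SAP 10.3, replace the single creatinine range with the laboratory's sex-specific limits. Alternatively, delete creatinine from the list so that it is flagged on laboratory-reported ranges like the unlisted analytes. State the source of the range, because the second option helps only if the laboratory's limits differ by sex.

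The cost is a wording change, with no new data. The downside is that laboratory-reported limits may vary, since Protocol 7.4.2 permits local laboratories in some circumstances. Sex-specific central-laboratory limits applied to all subjects would avoid this.

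Optional: one descriptive table of post-baseline eGFR and creatinine clearance, below 60 versus 60 mL/min or more, by baseline category, with the equations named. If it is added, show both any scheduled visit and two consecutive scheduled visits. There are 12 scheduled post-baseline visits (Months 1, 3, 6 and 12, then 8 more to Month 60). For a stable true eGFR of 65, an assumed within-subject CV of 5–8% and independent visits, the chance per visit of a value under 60 is Φ((60 − 65)/(CV × 65)) = 0.062–0.168. The chance of at least one in 12 is 1 − (1 − p)^12 = 54–89%, against 4–24% for two in a row.

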Overall, 424 adverse events (AEs) were reported in 88 subjects (49% in the BZF group and 51% in the placebo group). A total of 39 serious adverse events (SAEs) were reported in 26 subjects (28% in the BZF group and 24% in the placebo group). The most frequently reported AEs were arthralgia and myalgia. A total of 4 subjects (3 [6%] on BZF and 1 [2%] on placebo) had increases in aminotransferases that were more than 5x ULN and were significant enough to require treatment withdrawal. All AEs of elevated aminotransferases resolved within 3 months for the BZF subjects (spontaneously in 1 subject) or after administration of glucocorticoid (in 2 subjects with whom liver histologic features at baseline were suggestive of associated autoimmune hepatitis [AIH]) (Corpechot 2018).

Across all studies, BZF appeared to be well tolerated and the AEs reported in subjects with PBC were generally mild, affecting predominantly the gastrointestinal tract, skin, and musculoskeletal system. Impaired liver and kidney function have also been reported, albeit less frequently (<1%).

Refer to the latest version of the FDC Investigator's Brochure for additional information regarding the BZF clinical program.

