- Unscheduled visits as needed in the event of signs or symptoms of potential hepatic and/or muscular injury or decompensation or if laboratory alerts have been triggered

It is important that the laboratory assessments be completed as required and that the central laboratory be used for assessments whenever possible. In the event that a subject cannot return to the clinic for a scheduled or unscheduled visit, or there is an event that triggers a need for an immediate assessment, the use of a local lab is permissible at the discretion of the Investigator. In these cases, the Investigator will obtain the laboratory results and the laboratory normal ranges.

The process for assessing criteria is presented in Figure 2, and the specific threshold(s) for each laboratory analyte to trigger investigational product interruption are summarized in Table 5.

Figure 2: Management Algorithm for Potential Hepatic and/or Muscular Injury

CK=creatine kinase; INR=international normalized ratio; IP=Investigational Product; PK=pharmacokinetic

Notes: Laboratory assessments include: ALT, ALP, AST, GGT, direct and total bilirubin, INR, and CK.

PK sampling should be conducted within 7 days of IP interruption; close monitoring including physical exams and repeat biochemistry labs should occur as often as deemed appropriate by the Investigator (Table 4).

Table 4: Laboratory Criteria for Monitoring of Potential Hepatic and Muscular Injury for Interruption^a of Investigational Product

Baseline ^b	Treatment Emergent	Liver Signs and Symptoms ^c
Any value	Any hepatic enzyme elevation (TB, ALP, AST, ALT, GGT)	Yes
ALT or AST Normal	ALT or AST ≥ 3 x ULN and TB ≥ 2 x BL	Yes or No
	ALT or AST ≥ 3 x ULN and INR >1.5	Yes or No
	ALT or AST ≥ 5 x ULN and Any TB	Yes or No
ALT or AST Elevated	ALT or AST ≥ 2 x BL and TB ≥ 2 x BL	Yes or No
	ALT or AST ≥ 2 x BL and INR >1.5	Yes or No
	ALT or AST ≥ 3 x BL (or ≥ 300 U/L, whichever occurs first) and Any TB	Yes or No
TB \leq ULN	TB ≥ 2 x BL and $>$ ULN	Yes or No
TB $>$ ULN	TB ≥ 1.5 x BL or ≥ 3.0 mg/dL, whichever occurs first	Yes or No
ALP \leq ULN	ALP ≥ 2 x BL and $>$ ULN	Yes or No
ALP $>$ ULN	ALP ≥ 2 x BL or ≥ 1000 U/L, whichever occurs first	Yes or No
CK	≥ 5 x ULN or ≥ 3 x ULN with symptoms of rhabdomyolysis ^{d,e}	N/A

BL=baseline; CK=creatinine kinase; DILI=drug-induced liver injury; INR=international normalized ratio; IP=investigational product; N/A=not applicable; TB=total bilirubin

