14.2.6. Laboratory Assessments

Subjects should be instructed to fast overnight (at least 8 hours) before all study visits, but water is permitted. Record fasting status in the source and eCRF. If the subject reports having eaten or drunk anything other than water within 8 hours, document accordingly in the source and eCRF and remind the subject that fasting is required before all onsite study visits.

Blood and urine samples for laboratory assessments will be collected at the visits indicated in [Table 3](#).

Full instructions concerning the number and type of samples to be collected at each visit, the required sample volumes, sample collection methods, sample processing, labeling, and shipping will be provided in separate procedural manuals. All necessary collection supplies will be provided by the central laboratory and will be appropriately assembled for the specific evaluations required at each visit.

All subjects with laboratory tests containing CS abnormal values are to be followed regularly until the values return to normal ranges, until a valid reason (other than investigational product related AE) is identified, or until further follow-up is deemed medically unnecessary. Clinically significant changes as assessed by the Investigator in laboratory tests, not associated with a documented AE, should be recorded as AEs. An abnormal laboratory value should be deemed CS if either of the following conditions is met:

- The abnormality suggests a disease and/or organ toxicity that is new or has worsened from baseline.

- The abnormality is of a degree that requires additional active management, for example change of dose, discontinuation of drug, close observation, more frequent follow-up assessments, or further diagnostic evaluation.

Urine-based β -hCG pregnancy tests will be performed in female subjects of childbearing potential per protocol-specified visits. If a urine pregnancy test is positive, a quantitative serum pregnancy test must be performed to confirm the result. If positive, the Sponsor must be notified, and the subject will be followed as outlined in [Section 14.1.10](#) until pregnancy outcome.

CP, GLOBE, and UK-PBC scores will be calculated based on demographic, examination, and clinical laboratory values as described in the Statistical Analysis Plan (SAP).

MELD score will be calculated from serum chemistry and other parameters collected at the same visit with scores recorded on the eCRF.

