5.1. Baseline Definitions

The Baseline value for statistical analyses is defined as the last evaluations prior to the first administration of investigational product in Study 977-311, unless otherwise specified. For subjects under protocol amendment 2, the baseline value is defined as the evaluations on Day 1.

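### Apart from Hy's law, no visible SAP safety table counts subjects with graded rises in ALT/AST, ALP or CK, and the scheduled-visits rule can drop unscheduled peaks

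*SAP*

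**What the plan says.** SAP 10.3 plans descriptive statistics by visit, "shift tables (i.e., low-normal-high at Baseline versus low-normal-high at post-Baseline visit in a 3-by-3 contingency table", a summary of subjects meeting Hy's law, and listings. The shifts run "from Baseline to worst value, last value, and at each scheduled post Baseline visit". Hy's law is AST or ALT at least 3 times ULN together with total bilirubin at least twice ULN, at any timepoint.

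SAP 5.5 states: "Only the scheduled visits will be included in the analyses". Unscheduled visits go to listings.

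On baseline, SAP 5.1 says: "The Baseline value for statistical analyses is defined as the last evaluations prior to the first administration of investigational product in Study 977-311". SAP 10.3 says: "Baseline is defined as the mean of all available evaluations prior to the first administration of investigational product".

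Protocol section 7.4.2 contains Table 4, "Laboratory Criteria for Monitoring of Potential Hepatic and Muscular Injury for Interruption". Its single-analyte limits, with or without symptoms, are:

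- **ALT or AST:** at least 5 times ULN if normal at baseline; at least 3 times baseline or 300 U/L if elevated.
- **ALP:** at least twice baseline and above ULN if normal at baseline; at least twice baseline or 1000 U/L if elevated.
- **Total bilirubin:** at least twice baseline and above ULN if normal at baseline; at least 1.5 times baseline or 3.0 mg/dL if elevated.
- **CK:** at least 5 times ULN (3 times with symptoms of rhabdomyolysis).

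Footnote b resets the ALT, AST, ALP and bilirubin baseline to the Month 3 and Month 6 average when that average is more than 50% below the original.

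**The concern.** Long-term safety is the primary objective, and liver and muscle injury are among the named risks of the two components. The sites will act on graded laboratory limits, but the planned tables do not show how many subjects reached them. The categorical table has one cell for everything above normal, and Hy's law requires a bilirubin rise as well. Isolated ALT/AST rises, all ALP rises and all CK rises therefore have no graded count.

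The visit rule adds to this. After Month 12, scheduled laboratory tests are six months apart, whereas footnote a of Table 4 asks for repeat tests 2 to 3 times a week after a trigger. Peaks are therefore likely to fall at unscheduled visits, which SAP 5.5 leaves out of the tables.

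At stake is whether the report can state from its tables a number such as 0 of 133 with ALT at or above 5 times ULN, or must have it rebuilt from listings.

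**Working it through.** The plan states no figure to reproduce. The check compares planned tables with limits, using the ULNs in SAP 10.3: ALT and AST 45, ALP 122, CK 182 (female), 439 (male 18-50) and 331 (male 51-80) U/L; total bilirubin 12.3 µmol/L.

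**1. Limits in units**

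| Analyte | Multiple of ULN | Value |
|---|---|---|
| ALT/AST | 3, 5, 10 × 45 | 135, 225, 450 U/L |
| CK, female | 3, 5 × 182 | 546, 910 U/L |
| CK, male 51-80 | 3, 5 × 331 | 993, 1655 U/L |
| CK, male 18-50 | 3, 5 × 439 | 1317, 2195 U/L |
| Bilirubin (Hy's law) | 2 × 12.3 | 24.6 µmol/L |

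**2. What the planned tables show (hypothetical subjects)**

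| Subject | Multiple of ULN | Table 4 limit | Planned table shows |
|---|---|---|---|
| ALT 60 to 600, bilirubin normal | 600/45 = 13.3 | min(3 × 60, 300) = 180: met | high-to-high, not Hy's law |
| Female CK 200 to 2000 | 2000/182 = 11.0 | 910: met | high-to-high |
| ALT normal to 46 | 46/45 = 1.02 | 225: not met | normal-to-high |
| ALT normal to 450 | 450/45 = 10.0 | 225: met | normal-to-high |

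The last two share a cell. The first two are possible at entry: protocol 8.3 excludes ALT only above 5 times ULN, CK only at or above 5 times ULN, and sets no ALP limit. The documents do not give the share of subjects above ULN at entry.

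**3. Other outputs**

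- *Efficacy (SAP 9.1):* the ALP criteria count falls, not rises.
- *Adverse events:* protocol 14.2.6 says "Clinically significant changes as assessed by the Investigator in laboratory tests, not associated with a documented AE, should be recorded as AEs", and treats a value as clinically significant if it requires, for example, discontinuation or close observation. Most acted-on triggers should therefore become adverse events. Their severity is graded by limitation of activity (protocol Table 9), so a symptom-free ALT of 10 times ULN may be recorded as mild.
- *Drug action:* SAP 10.2.3 tabulates events leading to drug withdrawal, not interruption. SAP 10.1 counts dose increases and decreases, and uses interruptions only to subtract exposure days.
- *Special interest and adjudication:* hepatic injury is a MedDRA query, and the muscle category is the single term myalgia. Adjudication (protocol 14.3) covers hepatic and renal events, so CK is covered least directly.

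**4. Size**

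Assume a true rate of 1% to 6%. The 6% is the bezafibrate arm of the placebo-controlled trial in protocol 5.4.2 (3 subjects, against 1, or 2%, on placebo). Expected counts are 0.01 × 133 = 1.3 and 0.06 × 133 = 8.0. The exact (Clopper-Pearson) 95% interval for 8/133 = 6.0% is 2.6% to 11.5%. For 0/133 the two-sided upper limit is 1 − 0.025^(1/133) = 2.7%.

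**5. Baseline**

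If a subject has two pre-dose ALT values, 50 then 90, the last value gives min(3 × 90, 300) = 270 U/L. The mean, 70, gives min(3 × 70, 300) = 210 U/L. A later ALT of 240 meets one limit and not the other. This needs more than one pre-dose value; with a single Day 1 sample the two definitions agree.

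**The case against.** The strongest reply is that nothing the protocol promised is missing. Protocol 15.3 asks for descriptive statistics, Hy's law and shifts on normal ranges, and SAP 10.3 plans these for serum chemistry. Table 4 is a rule for managing patients, and neither document says it will be tabulated. This stands: a reader might infer a breach of the protocol's statistics section, and the documents do not support that.

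A reader might also infer that these events would go unseen. They would not. Values are in listings, each visit's maximum is in the descriptive statistics, acted-on triggers should be adverse events, and potential hepatic injury is adjudicated, with hepatic results going to the monitoring committee. The adjudication charters are not available, so whether they use laboratory limits is unknown. With 1 to 8 subjects, rebuilding the count by hand is feasible. None of these outputs, however, counts subjects at a limit.

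A third tempting reading is that the study will yield nothing like the published bezafibrate figure. That figure covers subjects who "had increases in aminotransferases that were more than 5x ULN and were significant enough to require treatment withdrawal". The table of events leading to withdrawal is a fair counterpart, though not defined by a threshold. Table 4 footnote e also says to discontinue at a CK of at least 5 times ULN, so some CK cases would enter that table, although protocol 5.6.3 and 7.4.4.3 say interrupt.

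The 6% rate may not transfer, because inclusion criterion 1 takes subjects already on investigational product. Finally, the specific wording of SAP 10.3 (worst value, any timepoint, central or local laboratories) could be read as overriding SAP 5.5. The SAP does not say so, and one sentence would settle it.

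**Conclusion.** The point holds as a gap in the visible SAP text; SAP 10.3 itself shows no redaction. Hy's law is the only safety count at a multiple of ULN, the three-category shifts cannot grade a rise, and SAP 5.5 applied as written removes unscheduled peaks from the worst-value shift and from Hy's law. The change should be made because it is cheap and improves the counts for the primary objective.

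The size is small in absolute terms: about 1 to 8 of 133 subjects, resting on an assumed 1% to 6% rate whose upper end may be too high for this population. A clean result is affected too, since the 2.7% upper limit for 0/133 also needs a count. The baseline discrepancy changes a count only for subjects with more than one pre-dose value.

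**What to change.** Amend SAP 10.3 as follows.

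1. State that the worst-value shift, Hy's law and the new tables use all post-baseline values, scheduled and unscheduled, central and local, as an exception to SAP 5.5.
2. Add n (%) of subjects by worst post-baseline value, cross-tabulated by baseline band: ALT and AST at ≥3, ≥5 and ≥10 times ULN; CK at ≥3 and ≥5 times ULN. Only a move to a higher band counts as treatment-emergent, so an unchanged ALT of 4 times ULN is not counted as a rise. The 10-times band is a reporting choice, not a Table 4 limit.
3. Add n (%) meeting each Table 4 single-analyte limit for ALT/AST, ALP and total bilirubin, and CK ≥5 times ULN, with all conditions kept. Without the above-ULN condition, for example, an ALP going from 50 to 100 U/L would count although it stays within 44-122.
4. Use the last pre-dose value (SAP 5.1) as the one laboratory baseline. In the table under item 3, apply the footnote b reset baseline where its condition is met.

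The cost is SAP wording, one or two extra tables, and derivation work to pool visit types and laboratories. No new data collection or protocol amendment is needed.
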